1.4 Rationale

The IMpower133 clinical trial evaluated chemotherapy and atezolizumab for first line treatment of patients with untreated ES SCLC. The results from the trial led to an FDA approval and established this regimen as a new standard of care. However, while patients with brain metastases were allowed, prior cranial radiation was required for these patients. Furthermore, only 9% of enrolled patients had brain metastases. There remains an urgent need to define clinical outcomes for patients treated with chemotherapy and atezolizumab with asymptomatic, untreated brain metastases.

Recent studies with systemic immunotherapy in brain metastases patients have demonstrated that outcomes for patients with and without brain metastases are generally similar. The IMpower133 study demonstrated PFS outcomes of 5.2 months for the atezolizumab arm versus 4.3 months for the placebo arm. Thus, we hypothesize that atezolizumab plus chemotherapy (i.e. carboplatin and etoposide) will improve intracranial progression free survival (iPFS) in patients with brain metastases from SCLC relative to historical controls (\geq 5.2 months vs. 4 months).

This study will enroll patients with asymptomatic brain metastases and untreated ES SCLC. Patients will be treated with combination carboplatin, etoposide, and atezolizumab. Restaging radiographic imaging will occur every 6 weeks (approximately every 2 cycles of treatment). At time of progression, patients can pursue standard of care treatment and radiation therapy off study. Our hypothesis is that the addition of atezolizumab will improve intracranial progression free survival in patients with untreated brain metastases. Furthermore, the study will provide valuable insight in the clinical outcomes of the patient population with ES SCLC and brain metastases. In general, chemotherapy response rates are expected to be high, and immune checkpoint therapy is known to have efficacy in other CNS malignancies. We believe treatment with systemic therapy alone will 1) delay time to WBRT 2) preserve quality of life longer 3) allow a subpopulation of patients to avoid WBRT and 4) be able to avoid a detrimental impact on survival given the close radiographic follow up.

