6.4 Protocol Therapy Discontinuation

In addition to discontinuation from therapy related to toxicities as outlined above, a subject will also be discontinued from protocol therapy and followed per protocol under the following circumstances outlined below. The reason for discontinuation of protocol therapy will be documented on the electronic case report form (eCRF)

- Documented disease progression based on RECIST 1.1
- Site investigator determines a change of therapy would be in the best interest of the subject
- Subject requests to discontinue protocol therapy, whether due to unacceptable toxicity or for other reasons
 - In a subject decides to prematurely discontinue protocol therapy (“refuses treatment”), the subject should be asked if he or she may still be contacted for further scheduled study assessments. The outcome of that discussion should be documented in both the medical records and in the eCRF.
- Female subject becomes pregnant
- Protocol therapy is interrupted for ≥ 63 days.

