- 4: CBC with platelet and differential (white blood cell count, absolute neutrophil count, hemoglobin and platelet count). Serum chemistries (creatinine, glucose, total bilirubin, aspartate transaminase [AST] and alanine transaminase [ALT] and calcium). Thyroid Function testing should be performed at screening then every 6 weeks (i.e. every other cycle). TSH will be obtained. T4 and T3 including free versus total testing is at the discretion of the site investigator. Hepatitis testing to be performed at screening if results as described in the inclusion criteria are not known. For women of childbearing potential (WOCBP): urine or serum β hCG if clinically appropriate. If a urine test is done and it is positive or cannot be confirmed as negative, a serum pregnancy test will be required. Testing is required within 24 hours prior to initiation of study treatment. During treatment, testing should be performed every 3 weeks (on Day 1 of each cycle prior to administering treatment).
- 5: Tumor response assessment will consist of evaluation by MRI scan of the brain and CT scans of chest +/- abdomen and pelvis. If unable to perform MRI due to medical reasons, CT with contrast is acceptable. Brain MRI used to diagnose brain metastases allowed or a CT with contrast is acceptable. The abdomen/pelvis may be scanned at follow-up timepoints only if positive disease was detected at baseline. Radiology imaging to be performed at screening (within 6 weeks prior to C1D1), then every 6 weeks (prior to Cycle 3 Day 1 and Cycle 6 Day 1) then every 9 weeks (prior to Cycle 9 and so on). Imaging needs to occur every time point regardless of any delay in treatment. Tumor imaging to be done in the follow up period is at discretion of site investigator. If tumor assessments are available for subjects who have not yet experienced progressive disease (PD) at the time treatment is discontinued, the follow-up tumor evaluations will be documented in the eCRF until PD or death is confirmed, or until another treatment is initiated.
- 6: Induction treatment will consist of 4 cycles of Atezolizumab (1200 mg on Day 1) combined with carboplatin (5-6 AUC on Day 1) and etoposide (80-100 mg/m² on Days 1-3). After 4 cycles of induction treatment, subjects will receive atezolizumab maintenance 1200 mg on Day 1 of each 3-week cycle. Subjects will receive treatment until disease progression, unacceptable drug-related toxicity, or withdrawal from study for any reason.

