9.2.5 Evaluation of best overall CNS response

Target Lesions	Non-Target Lesions	New Lesions**	Corticosteroids	Clinical status	Overall Response
None	None	None	None	Stable or improved	CR
≥30% decrease in sum longest distance relative to baseline	Stable or improved	None	Stable or decreased	Stable or improved	PR
<30% decrease relative to baseline but <20% increase in sum longest distance relative to nadir	Stable or improved	None	Stable or decreased	Stable or improved	SD

$\geq 20\%$ increase in sum longest distance relative to nadir*	Uequivocal progressive disease*	Present*	N/A	Worse*	PD

*Progression occurs when any of these criteria are met. If ≤ 6 months from initiation of immunotherapy, radiographic progression (including new lesions) with no new or significantly worsened neurologic deficits not due to co-morbid event or concurrent medication should be confirmed on follow-up imaging 3 months after initial radiographic progression (if progression confirmed, the date of actual progression should be back-dated to the date of initial radiographic progression). **A new lesion is one that is not present on prior scans and is visible in minimum two projections. If a new lesion is equivocal, for example because of its small size, continued therapy can be considered, and follow-up assessment will clarify if the new lesion is new disease. If repeat scans confirm there is definitely a new lesion, progression should be declared using the date of the initial scan showing the new lesion.
					

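### Section 9.2.5 does not say how to date early brain progression when the 3-month confirmatory scan is missing or is taken after new treatment

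*Combined protocol and SAP*

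**What the plan says.** The primary endpoint (Sections 2.2.1 and 12.2.1) is the time from Day 1 of treatment to RANO-BM intracranial progression or death from any cause. The footnote to the response table in Section 9.2.5 therefore dates the primary endpoint. It applies "If ≤ 6 months from initiation of immunotherapy" to radiographic progression, new lesions included, "with no new or significantly worsened neurologic deficits not due to co-morbid event or concurrent medication". Such progression "should be confirmed on follow-up imaging 3 months after initial radiographic progression (if progression confirmed, the date of actual progression should be back-dated" to the first scan. Nothing is said about a case that is never rescanned, or is rescanned only after other treatment.

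Several other sections bear on whether that scan happens:

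- Section 6.4 ends protocol therapy at "Documented disease progression based on RECIST 1.1", with no confirmation step. Under Section 9.1.5 a new lesion is RECIST progression.
- Section 1.4: "At time of progression, patients can pursue standard of care treatment and radiation therapy off study".
- Section 7, footnote 11, schedules survival follow-up only, once progression is documented. Nine-weekly imaging is for patients who stop for other reasons, and it ends at progression or new treatment.
- Section 9.2 runs brain MRI until progression is documented.
- Section 7, footnote 5, leaves follow-up imaging to the site. For patients without progression at discontinuation, it records evaluations "until PD or death is confirmed, or until another treatment is initiated".

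The only written censoring sentence, in Section 12.2.2, is for PFS. None is written for iPFS.

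**The concern.** The confirmation rule assumes that the patient is still imaged, and not yet treated with something else, 3 months after the first progressing scan. For a new brain lesion the other sections point the opposite way: therapy stops, other treatment may begin, and scheduled brain imaging ends. Some patients will also die first. A scan taken after cranial radiotherapy or second-line therapy may show shrinkage and so appear to refute a true progression.

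The handling of these cases is then left to whoever derives the endpoint, possibly after the data are known. Two of the three available readings make iPFS longer. There is no concurrent control arm to share the bias, and the targeted gain is only 1.2 months (5.2 against 4.0, Section 12.3). The futility look in Section 12.7, at about 29 events, depends mainly on early events, which is where the rule applies.

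**Working it through.** **1. The plan's own figures.** Inputs from Section 12.3: medians 4.0 and 5.2 months, 60 patients, one-sided 0.15, 22 months of accrual, 12 months of follow-up, exponential survival, 58 events, about 81% power.

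- Simple approximation: Φ(√58 × ln(5.2/4.0) − 1.036) = Φ(7.616 × 0.262 − 1.036) = 0.83.
- One-sample logrank formulas with 12 months of follow-up: 0.80 to 0.82. The stated power is reproduced.
- Side note: the stated event probability of 0.9707 corresponds to 18 months of follow-up; 12 months gives 0.9348 (56.1 events). This does not affect the point.

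**2. How many events the rule can reach.** P(T ≤ 6) = 1 − 2^(−6/4.0) = 0.65, or about 39 of 60 patients, under the null. At a 5.2-month median it is 1 − 2^(−6/5.2) = 0.55, or about 33. This is a ceiling, because deaths and symptomatic progressions need no confirmation.

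**3. Assumptions that the documents do not supply.**

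- Share of first iPFS events that are asymptomatic radiographic progression: 30 to 50%. The rule then reaches 0.65 × 30% to 0.65 × 50%, about 19 to 32% of patients.
- Share of the early ones never confirmed: 25 to 50%. Patients affected: 60 × 0.646 × 0.30 × 0.25 = 2.9, up to 60 × 0.646 × 0.50 × 0.50 = 9.7.
- Median survival after progression: 3 to 7.1 months. The upper value is 12.3 − 5.2, the IMpower133 atezolizumab-arm medians in Section 1.2. The placebo-arm figures give 10.3 − 4.3 = 6.0.

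**4. Simulation.** True median 4.0 months, 60 patients, uniform accrual over 22 months plus 12 months, 20,000 runs. Test: Z = (O − E)/√E, where E is the sum of (ln 2/4.0) × time at risk; reject if Z < −1.036. With every progression dated to its first scan, the rejection rate is 0.14 (nominal 0.15).

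Unconfirmed cases moved to the date of death:

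| Radiographic share | Unconfirmed share | Median survival after progression (months) | Patients moved | Apparent median iPFS (months) | False-positive rate |
|---|---|---|---|---|---|
| 30% | 25% | 3 | 2.9 | 4.3 | 0.21 |
| 30% | 50% | 3 | 5.8 | 4.6 | 0.29 |
| 50% | 50% | 3 | 9.7 | 5.0 | 0.43 |
| 30% | 25% | 7.1 | 2.9 | 4.4 | 0.32 |
| 50% | 50% | 7.1 | 9.7 | 5.5 | 0.80 |

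Unconfirmed cases censored at the first scan instead: 0.24 with the shares of the first row and 0.59 with those of the third.

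**5. Death as the only cause of a missing scan.** The share dying within 3 months is 1 − 2^(−3/m): 50% for m = 3 and 25% for m = 7.1. Each delay is then under 3 months. The false-positive rate is 0.17 at 30% radiographic and m = 3, and about 0.15 to 0.20 over the whole range.

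The larger figures therefore come from patients who are alive but not rescanned. The model also lets them have no iPFS event before death. A later neurologic worsening, or a progression after 6 months, would need no confirmation; if recorded, it would shorten the delay.

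**The case against.** The strongest reply is that the documents nowhere move an unconfirmed progression to death or censor it. The Section 9.2.5 footnote opens by treating any one of the listed criteria as progression, and it back-dates if confirmed, not only if confirmed. Counting an unrefuted first scan as the event is an equally literal reading. That stands. A reader might infer that real progressions are lost under this plan, but the text is silent and the defect is the silence.

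Four further points also stand:

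- Footnote 5 concerns patients without progression at discontinuation, so it does not by itself end documentation for those stopped for RECIST progression.
- Section 1.4 permits off-study treatment; it does not require it.
- Brain growth is not always RECIST progression. RECIST takes at most two targets per organ and five in all (Section 9.1.3), so 20% growth in the brain sum need not be 20% overall. The link is secure only for new lesions. Where RECIST progression is not met, Section 6.4 does not stop therapy on that ground and brain MRI goes on.
- The survival values are rough. A difference of two medians is not a median survival after progression, and the source trial had 9% of patients with brain metastases and required prior cranial radiation for them.

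Confirmation has a purpose: Section 9.2 notes that imaging after immunotherapy behaves differently. But that does not supply a rule for the unconfirmed case. New lesions show the conflict most clearly. Section 9.2.4 says that on immunotherapy they may not alone be progression, while Sections 9.1.5 and 6.4 make them a reason to stop.

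**Conclusion.** The point holds as a gap in the primary endpoint definition, and it is more than missing detail. For early asymptomatic progression, new lesions above all, the protocol's other rules make the required scan unlikely or leave it open to treatment effects, and no fallback is written. Under either of the two readings that do not count the first scan, the bias favours the treatment.

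Its size is uncertain. On the assumed shares, with cases moved to death, the false-positive rate goes from about 0.14 to 0.21 or more: 0.29 at 30%/50%/3 months, and higher with longer assumed survival after progression. It is only about 0.15 to 0.20 if death within 3 months is the sole cause of missing scans.

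Two stronger conclusions are tempting and unsupported. One is that the rule governs 65% of iPFS events; that is a ceiling before deaths and symptomatic progressions are removed. The other is that the error rate will reach 0.80; that figure needs the least favourable combination of shares and survival, and the documents supply none of them. The change should be made before the primary analysis.

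**What to change.** In Section 9.2.5, with a matching derivation rule in Section 12:

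- Date iPFS to the first scan showing progression, unless a later brain scan, taken before any cranial radiotherapy or new anti-cancer therapy, shows that progression was not confirmed.
- Count progression left unconfirmed through death, a switch of therapy, withdrawal or a missing scan at the first-scan date.
- Write an explicit iPFS censoring rule.
- Add a sensitivity analysis with the alternative handling (event at death, and censoring).

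Sections 1.4, 6.4, 7 (footnotes 5 and 11), 9.2, 9.2.4 and 9.2.5 must be reconciled on confirmation, imaging, and treatment while confirmation is pending. Which clinical rule applies is for the investigators, and none is proposed here.

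The cost is one footnote, one derivation rule and one extra analysis. The dating rule needs no new scans. In the simulation, dating every early progression to its first scan gives a false-positive rate of 0.14. The downside is that an occasional pseudo-progression, in a patient who switches or is not rescanned, will count as an event. That error is conservative.

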10 DRUG INFORMATION

All drugs used in this clinical trial will be standard of care. Please refer to the latest version of the prescribing information that can be found at <http://www.accessdata.fda.gov/scripts/cder/drugsatfda/>, and/or each manufacturer's website.

10.1 Atezolizumab

PD-L1 may be expressed on tumor cells and/or tumor infiltrating immune cells and can contribute to the inhibition of the anti-tumor immune response in the tumor microenvironment. Binding of PD-L1 to the PD-1 and B7.1 receptors found on T cells and antigen presenting cells suppresses cytotoxic T-cell activity, T-cell proliferation and cytokine production. Atezolizumab (TECENTRIQ®) is a monoclonal antibody that binds to PD-L1 and blocks its interactions with both PD-1 and B7.1 receptors. This releases the PD-L1/PD-1 mediated inhibition of the immune response, including activation of the anti-tumor immune response without inducing antibody dependent cellular cytotoxicity. In syngeneic mouse tumor models, blocking PD-L1 activity resulted in decreased tumor growth.

Please refer to the current version of the Investigator's Brochure (IB) for additional information regarding this drug.

10.1.1 Supplier/How Supplied

GNE will supply atezolizumab at no charge to subjects participating in this clinical trial. Atezolizumab Injection, 1200 mg/20 mL (60 mg/mL). Atezolizumab is provided in a single-use, glass vial as a colorless-to-slightly-yellow, sterile, preservative-free clear liquid solution intended for IV administration. The vial is designed to deliver 20 mL (1200 mg) of atezolizumab solution but may contain more than the stated volume to enable delivery of the entire 20 mL volume. The atezolizumab Drug Product is formulated as 60 mg/mL atezolizumab in a solution containing histidine acetate, sucrose, and polysorbate 20 at pH 5.8.

The site investigator shall take responsibility for and shall take all steps to maintain appropriate records and ensure appropriate supply, storage, handling, distribution, and usage of investigational product in accordance with the protocol and any applicable laws and regulations.

10.1.2 Preparation

Visually inspect drug product for particulate matter and discoloration prior to administration, whenever solution and container permit. Discard the vial if the solution is cloudy, discolored, or visible particles are observed. Do not shake the vial. Prepare the solution for infusion as follows:

- Select the appropriate vial(s) based on the prescribed dose.
- Withdraw the required volume of atezolizumab from the vial(s).
- Dilute into a 250 mL polyvinyl chloride (PVC), polyethylene (PE), or polyolefin (PO) infusion bag containing 0.9% Sodium Chloride Injection, USP.
- Dilute with only 0.9% Sodium Chloride Injection, USP.
- Mix diluted solution by gentle inversion. Do not shake.

10.1.3 Storage and Stability

Storage of Infusion Solution: This product does not contain a preservative. Administer immediately once prepared. If diluted Atezolizumab infusion solution is not used immediately, store solution either:

- At room temperature for no more than 6 hours from the time of preparation. This includes room temperature storage of the infusion in the infusion bag and time for administration of the infusion, or
- Under refrigeration at 2°C to 8°C (36°F to 46°F) for no more than 24 hours from time of preparation.
- Do not freeze or shake

10.1.4 Dispensing

Atezolizumab must be dispensed only from official study sites and to eligible subjects under the supervision of the site investigator. Atezolizumab should be stored in a secure area according to local regulations. It is the responsibility of the site investigator to ensure that study drug is only dispensed to subjects.

10.1.5 Adverse Events

Please refer to the latest version of the prescribing information that can be found at <http://www.accessdata.fda.gov/scripts/cder/drugsatfda/>, and/or on the manufacturer's website.

10.2 Carboplatin and Etoposide

Carboplatin and etoposide will be used as standard of care in the study and sourced commercially.

For information regarding these medications, please refer to the latest version of the prescribing information that can be found at <http://www.accessdata.fda.gov/scripts/cder/drugsatfda/>, and/or on the manufacturer's website.

11 ADVERSE EVENTS

11.1 Definitions

11.1.1 Adverse Event (AE)

An AE is any untoward medical occurrence whether or not considered related to the study drug that appears to change in intensity during the course of the study. The following are examples of AEs:

- Unintended or unfavorable sign or symptom (including an abnormal laboratory finding)
- A disease temporally associated with the use of an investigational medicinal product (IMP) or other protocol-imposed intervention, regardless of attribution
- An intercurrent illness or injury that impairs the well-being of the subject
- AEs not previously observed in the subject that emerge during the protocol-specified AE reporting period, including signs or symptoms associated with extensive stage Small Cell Lung Cancer (SCLC) with untreated asymptomatic brain metastases that were not present prior to the AE reporting period.
- Complications that occur as a result of protocol-mandated interventions (e.g., invasive procedures such as cardiac catheterizations)
- If applicable, AEs that occur prior to assignment of study treatment associated with medication washout, no treatment run-in, or other protocol-mandated intervention.
- Preexisting medical conditions (other than the condition being studied) judged by the investigator to have worsened in severity or frequency or changed in character during the protocol-specified AE reporting period.

Hospitalization for elective surgery or routine clinical procedures that are not the result of an AE (e.g., surgical insertion of central line) should not be recorded as an AE.

Disease progression should not be recorded as an AE, unless it is attributable to the study regimen by the site investigator.

11.1.2 Serious Adverse Event (SAE)

A SAE is an adverse event that:

- Results in death. **NOTE:** Death due to disease progression should not be reported as a SAE, unless it is attributable by the site investigator to the study drug(s)
- Is life-threatening (defined as an event in which the subject was at risk of death at the time of the event; it does not refer to an event which hypothetically might have caused death if it were more severe)
- Requires inpatient hospitalization for >24 hours or prolongation of existing hospitalization. **NOTE:** Hospitalization for anticipated or protocol specified procedures such as administration of chemotherapy, central line insertion, metastasis interventional therapy, resection of primary tumor, or elective surgery, will not be considered serious adverse events.
- Results in persistent or significant disability/incapacity (i.e., the AE results in substantial disruption of the subject's ability to conduct normal life functions).
- Results in a congenital anomaly or birth defect in a neonatal/infant born to a mother exposed to IMP.

- Is an important medical event (defined as a medical event(s) that may not be immediately life-threatening or result in death or hospitalization but, based upon appropriate medical and scientific judgment, may jeopardize the subject or may require intervention (e.g., medical, surgical) to prevent one of the other serious outcomes listed in the definition above). Examples of such events include, but are not limited to, intensive treatment in an emergency room or at home for allergic bronchospasm; blood dyscrasias or convulsions not resulting in hospitalization; or the development of drug dependency or drug abuse.

